Impact of protein and alkali supplementation on skeletal muscle in older adults - Statistical Analysis Plan

Protocol Apr 10, 2022

SAP May 23, 2024

NCT ID NCT04048616

1. SAP purposes

This document provides a detailed description of the analysis plan for the Protein & Alkali trial. This document is meant to be used in conjunction with the study protocol. This document does not subsume the protocol, but several elements of the protocol, such as the sample size justification are reproduced here. This document:

1. Provides a written agreement between the investigators, trial statisticians, and data analysts regarding the analyses to be performed.
2. Provides a record of the analysis plan specified prior to examining any outcome data by group.
3. Provides clear specifications for the data analysts performing variable derivations, statistical analyses, and generating reports.

This document follows the guidance published by Gamble et al. in JAMA 2017.

2. SAP contributors and signatures

[name]

[name] MS

3. Introduction

a. *Background and rationale*

With aging, skeletal muscle mass and performance decline leading to an increased risk of falls and physical disability. There is ongoing research on whether increasing dietary protein intake in older adults improves indices of muscle health and thus translates to a reduction in physical disability. A main concern is that high protein results in a large dietary acid load from the breakdown of protein to acidogenic byproducts, which could in turn promote muscle degradation particularly in older adults with age-related declines in renal excretion of acid. The scientific premise of this project is that the balance between the amount of protein in the diet (anabolic component) and the net acid load of the diet (catabolic component) in part determines whether the diet as a whole has a net anabolic or catabolic effect on muscle. Preliminary data have suggested that a daily alkaline salt supplement (potassium bicarbonate, KHCO_3) lowered the dietary acid load and improved lower extremity muscle power in postmenopausal women.

The investigator's central hypothesis is that higher protein intake and a neutralizing alkaline salt will improve muscle performance and mass, compared to their respective placebos, in older men and postmenopausal women. To test the hypothesis, the investigators conducted a randomized, double-blind, placebo-controlled, 2x2 factorial study in underactive men and women age 65 and older on baseline lower protein diets. Participants were assigned to one of four groups: either a whey protein (WP) supplement (to raise protein intake to 1.5 g/kg/d) with or without potassium bicarbonate (KHCO_3) 81 mmol/d or an isocaloric placebo supplement with or without KHCO_3 81 mmol/d for 24 wks.

b. *Objectives*

Primary aim: Evaluate the effects of whey protein (WP) and of KHCO_3 on lower extremity muscle power at 24 weeks. This factorial ("at-the-margins") analysis will evaluate the effects of WP vs. placebo-WP and of KHCO_3 vs. placebo- KHCO_3 by using an ANCOVA approach comparing the primary outcome between groups with adjustment for baseline lower extremity muscle power, sex, age and factorial design.

Secondary aims: Evaluate the effects of WP and of KHCO_3 in terms of lower extremity muscle power at 12 weeks, knee extension torque at 12 and 24 weeks, physical performance at 24 weeks, lean mass at 24 weeks, handgrip strength at 24 weeks, physical performance battery at 24 weeks, and 24-hr urinary nitrogen excretion (UNi).

4. Study Methods

a. *Trial design*

This is a single-center, individually randomized, 2x2 factorial, placebo-controlled trial.

Participants were randomized in a 1:1:1:1 fashion to:

- whey protein isolate + KHCO_3
- whey protein isolate + microcrystalline cellulose
- maltodextrin powder + KHCO_3
- maltodextrin powder + microcrystalline cellulose

b. *Randomization*

Randomization was stratified by sex, by using block randomization (randomly permuted block sizes of 4 or 8). The random allocation sequence was computer-generated by a biostatistician. The randomization sequence was incorporated into the online Electronic Data Capture system. Central randomization via the online EDC system maintained allocation concealment.

c. Sample size

Sample size calculations focused on the change from baseline to 24 weeks in muscle power and were conducted for a factorial analysis (at-the-margins analysis), i.e. a) the comparison between all participants allocated to KHCO₃ vs. all those not allocated to KHCO₃ and b) the comparison between all participants allocated to whey protein vs. all those not allocated to whey protein. We will test each of these two primary hypotheses with a two-sided test and significance level 0.05. There will be no adjustment for multiplicity because, under the assumption of no interaction (the effect of whey protein is the same whether the patient is allocated to KHCO₃ or not, and similarly for KHCO₃), that is inherent to a factorial analysis, our trial answers two distinct research questions, and statistical simulation support that no adjustment is needed in this scenario. All secondary and exploratory analyses are considered as supporting the primary analysis, with two-sided tests and significance levels of 0.05.

Table 1 shows the hypothesized mean changes in muscle power in each of the 4 randomization groups. For the comparison of KHCO₃ vs. no KHCO₃, the hypothesized mean change is 10% (with) and 4% (without). We assumed a common standard deviation (SD) of change in power to be approximately 12%, based on the subset of men and women over age 65 in a previous study of the effect of HCO₃⁻(1). Sample sizes of 60 and 60 in KHCO₃ vs. no KHCO₃ yield 80% power to detect a between-group difference of at least 6%. This effect size was observed in the subset of older men and women in the previously referenced study (1). For the comparison of whey protein vs. no whey protein, the hypothesized mean change in muscle power from baseline to follow-up is 11% (with) and 3% (without). We assumed a common SD of change in power to be 15%. Sample sizes of 60 and 60 in whey protein vs. no whey protein yield 80% power to detect a between-group difference of at least 8%. This effect size was observed when subjects in the previous study (1) were divided into high and low protein groups based on their self-selected diets.

Table 1: Hypothesized change in leg power by intervention

		KHCO ₃		
		yes	No	Overall
Whey protein	Yes	14% N=30	8% N=30	N=60
	No	6% N=30	0% N=30	N=60
	Overall	N=60	N=60	

d. Framework

For all objectives, we use a superiority framework and a factorial analysis (at-the-margins analysis), i.e., testing the superiority of whey protein against no whey protein and of KHCO₃ against no KHCO₃.

e. Statistical interim analyses and stopping guidance

No formal statistical interim analysis was planned. The Data and Safety Monitoring Board (DSMB) periodically evaluated enrollment data, AE, and SAE by randomization group.

f. Timing of final analysis

Final analysis will take place after all data for the primary and secondary outcomes have been collected, data cleaning is complete, and after this SAP is finalized and posted on clinicaltrials.gov.

g. Timing of outcome assessments

Outcomes are measured at baseline, 12 weeks, and 24 weeks after randomization.

5. Statistical Principles

a. Confidence intervals and P values

All statistical tests will be 2-sided. We will use $p \leq 0.05$ to indicate statistical significance for the primary outcome for each of the two primary comparisons of interest in a factorial analysis (at-the-margins analysis): a) the comparison between all participants allocated to KHCO₃ vs. all those not allocated to KHCO₃ and b) the comparison between all participants allocated to whey protein vs. all those not allocated to whey protein. Under the assumption of no interaction that is inherent to a factorial analysis, the primary analyses test two independent hypotheses, and no multiplicity adjustment is needed in this scenario. All secondary and exploratory analyses are considered as supporting the primary analyses, with two-sided tests and significance levels of 0.05.

b. Adherence and protocol deviations

Adherence to study pills was assessed by capsule counts and by capsule diaries. Adherence to the protein packets was assessed by packet counts and diaries. Objective measures of adherence are urinary net acid excretion (NAE) and UNi.

Major protocol deviations for the trial include:

1. Participant found ineligible after randomization
2. No informed consent signed
3. Participant didn't receive the randomly allocated intervention
4. Withdrawal of consent for future data collection, and/or ongoing use of previously collected study data

c. Analysis populations

The full analysis set will include all randomized subjects. Following the intention-to-treat (ITT) principle, subjects will be analyzed according to the group they were assigned to at randomization regardless of treatments received.

In a modified ITT analysis set, we will exclude from the ITT sample those participants who –took less than 10% of whey protein isolate or KHCO₃ and those with any major protocol deviation.

In a per protocol analysis set, we will further restrict the mITT sample to participants who took whey protein isolate and KHCO₃ throughout the 24 weeks with an average compliance of at least 75%.

6. Trial Population

a. Eligibility

The inclusion criteria are:

- ambulatory community-dwelling men and women age ≥ 65 years
- habitual dietary intake of protein of ≤ 0.8 g/kg/d and not be vegetarian

- willing not to change their habitual diet, habitual exercise regimen, or enter into a weight loss program during the 24-wk study
- underactive based on the validated Rapid Assessment of Physical Activity (RAPA)
- estimated GFR $\geq 50 \text{ ml/min}/1.73 \text{ m}^2$

Participants who are taking a daily calcium supplement (as carbonate, acetate, citrate) can participate in the trial if they are willing to switch to a calcium triphosphate supplement provided to them by the study.

The exclusion criteria are

- users of the following medications or supplements:
 1. oral glucocorticoid use for > 10 days in the last 3 months
 2. anabolic and gonadal hormones in the last 6 months
 3. Tamoxifen/raloxifene in the last 6 months
 4. regular use of alkali-producing antacids (> 3 times per week)
 5. potassium containing supplements or products (i.e., KCl or salt substitutes)
 6. NSAIDS >3 times per week
 7. antacids containing calcium carbonate, aluminum hydroxide, magnesium hydroxide, or calcium acetate
 8. insulin
 9. sulfonylureas
 10. SGLT2 inhibitors
- individuals with the following conditions/diseases:
 1. a lower extremity fracture in the last year
 2. kidney stones in the past 5 years
 3. creatinine clearance $< 50 \text{ ml/min}$ (MDRD equation)
 4. hyperkalemia (serum potassium $>5.3 \text{ mEq/L}$; normal range 3.5-5.3 mEq/L)
 5. elevated serum bicarbonate ($>33 \text{ mmol/L}$; normal range 21-33 mmol/L)
 6. serum calcium outside the range of 8.3-10.2 mg/dl
 7. uncontrolled diabetes mellitus (fasting blood >150 or hemoglobin A1c $>8\%$)
 8. untreated thyroid or parathyroid disease
 9. significant immune disorder
 10. current unstable heart disease
 11. Crohn's disease
 12. active malignancy or cancer therapy in the last year
 13. alcohol use exceeding 2 drinks/day
 14. current peptic ulcers or esophageal stricture
 15. milk protein allergy
 16. other condition or abnormality in screening labs, at discretion of the study physician

b. Recruitment

We will use a CONSORT flow diagram to summarize the number of participants who:

- were assessed for eligibility at screening
- were eligible at screening
- were invited to participate
- provided consent
- were randomized
- withdrew prior to receiving treatment

- included in the primary analyses

The flow diagram will also show the numbers who were eligible but not randomized, who did not receive the randomized allocation, who discontinued the intervention, and we will describe the reasons.

c. Withdrawal/follow-up

The level of withdrawal will be tabulated and classified as “consent to continue follow-up and data collection”, “consent to continue data collection only”, “complete – no further follow-up or data collection”. The numbers (with reasons) of losses to follow-up (drop-outs and withdrawals) over the course of the trial will be summarized by randomization group.

d. Baseline patient characteristics

Participants will be described at the time of randomization with respect to age, sex, race and ethnicity, weight, BMI, blood pressure, physical activity assessment, DXA lean tissue mass, D₃-creatine dilution, double leg press power testing, knee extensor strength, handgrip strength, modified SPPB, total energy intake, dietary protein intake, and fruit and vegetable intake. All characteristics will be first tabulated overall and separately for whey protein vs. no whey protein and KHCO₃ vs. no KHCO₃. We will then tabulate the characteristics in each of the four cells of the 2x2 design. Categorical data will be summarized by numbers and percentages, and continuous data by mean, SD (or median, Q1-Q3 if data are skewed). No tests of statistical significance will be performed; any imbalance of clinical importance will be noted.

7. Analysis

a. Outcome definitions

Primary outcome: Keiser double leg press power at 70% at 24 weeks. Following one-repetition maximum measurement (1RM), the participant performs 5 presses at 70% of their 1RM as fast as possible through their full range of motion. The highest power output is determined to be the peak power.

Secondary outcomes:

- Double leg press peak power at 70% of 1RM at 12 weeks
- Double leg press peak power at 40% of 1RM at 12 and at 24 weeks
- Knee extension peak torque at 60°/sec at 12 and 24 weeks
- Maximum handgrip strength at 24 weeks
- Appendicular lean mass/ht² by DXA at 24 weeks
- Health ABC-PPB score at 24 weeks
- 24hr urinary nitrogen excretion

Exploratory:

- muscle mass as measured by D₃-creatine dilution at 24 weeks

b. Analysis methods

Summary statistics. For each outcome, we first will report summary statistics at each timepoint for whey protein vs. no whey protein and for KHCO₃ vs. no KHCO₃. We will then report summary statistics in each of the four cells of the 2x2 design. We also will create box plots that display the distribution of the data at each time point for each comparison.

Primary Outcome. Primary analyses of the primary outcome will be performed on the ITT sample based on an ANCOVA comparing 24-week leg power with fixed effects for intervention groups and further adjustment for leg power at baseline, age and sex. Moreover, the effect of each intervention will be adjusted for the other intervention. Type III sum-of-squares will be used to test significance of each intervention. Least squares mean difference between intervention groups, and 95% confidence intervals, based on the fitted linear models will be reported.

Table 2: Presentation of the results of the primary analyses

	Whey protein	No whey protein	KHCO ₃	no KHCO ₃
Leg power, mean (SD)	xx.x (xx.x)	xx.x (xx.x)	xx.x (xx.x)	xx.x (xx.x)
LS mean difference (95% CI)*		-xx.xx (-xx.x to -xx.x)		-xx.xx (-xx.x to -xx.x)
p value		xxx		Xxx

*adjusted for sex, age, leg power at baseline, and factorial design

Secondary analyses and secondary outcomes.

- We also will conduct factorial analyses of all secondary outcomes by using similar analytic approach to the primary outcome.
- In addition of ANCOVA analyses, we will fit longitudinal model based on all repeated measurements of the outcome, i.e., a linear model with 12-week and 24-week measurements as outcome observations and fixed effects for the intervention group, time treated as categorical, intervention group by time interaction, baseline measure, baseline measure by time interaction, and sex. The corresponding treatment effect measure is the between-group difference in the slopes of the mean responses. Restricted maximum likelihood estimation will be used with the Newton–Raphson algorithm. An unstructured covariance matrix will be used to model the variance-covariance matrix for random intercept and random slope. In the case of nonconvergence with UN, a toeplitz covariance matrix will be used. In the case of nonconvergence with TOEP, an autoregressive covariance matrix [AR (1)] will be used.

Difference in estimated least square mean slopes, the corresponding 95% CI, and p-value will be reported. We will use the p value from the type III F-test of the fixed effect parameter for the intervention group by time interaction. Denominator degrees of freedom will be estimated using the Kenward-Roger approximation with an unstructured covariance matrix and the between-within method otherwise.

- We also will present results for outcome measures at follow-up within each of the four factorial groups in the 2×2 design. We will test for interaction by extending the multivariable linear models described above by simply adding the appropriate interaction terms. However, we anticipate insufficient precision on the interaction estimates to rule out interaction.
- We will repeat analyses in the mITT and per protocol samples.

c. Subgroup Analyses

We will perform subgroup analyses by sex, NAE (<15 mmol/day vs. ≥ 15 mmol/day), protein intake based on average 3-day food recall (≤ 0.8 gm/kg/day vs. > 0.8 gm/kg/day), no sarcopenia vs. sarcopenia (defined as maximum grip strength <35.5 kg (men) and <20 kg (women) in either hand and/or gait speed <0.8 m/sec.

d. Missing data

Descriptive tables of baseline characteristics stratified by arm will include the frequency and percentage of missing values. In attrition analyses, we will then compare these variables between subjects who drop out and subjects with complete outcome data. The number of missing primary outcome data points at each time point, by intervention arm, will be reported in the CONSORT participant flow diagram.

For the primary analyses, we will analyze all available follow-up outcome data using restricted maximum likelihood estimation, under the assumption that data are missing at random.

As sensitivity analyses, we will use multiple imputation. Multiply imputed datasets will be generated by using imputation by chained equations. We will use predictive mean matching and logistic regression to impute continuous and binary outcomes, respectively. We will consider fully conditional specification. We will treat repeated measurements as distinct variables, so longitudinal data will be in wide format, with one row per participant, so that the within-subject correlation is maintained. We will impute at least 10 imputed datasets or a larger number corresponding to the fraction of missing outcome data. Randomization group, stratification factors, baseline variables, and outcome data will be considered for inclusion in the imputation model as auxiliary variables. We will compare the distribution of observed and imputed values to assess the adequacy of the imputation model. We will fit the linear models on each imputed dataset and combine results according to Rubin's rules. Depending on the amount and pattern of missing data, we will consider alternative strategies to handling missing data.

e. Harms

We will summarize the number and percentage of participants experiencing adverse events, both for the overall safety population and in each randomization group. We will not perform statistical testing. We will assess the clinical significance of the differences.

f. Statistical software

Analyses will be carried out using R and SAS.

References:

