[name] will ensure that study documents are stored in a manner that protects the privacy of subjects and the confidentiality of study data. The participants’ private information will be kept confidential, and access to this information will be restricted to the investigators and staff who are directly involved with the participants. Authorized regulatory personnel have the right to inspect and copy all records pertinent to this study. All data used in the analysis and reporting of this evaluation will have no identifiable reference to participants.

Protection and management of data: All information and materials will be obtained for research purposes only and the data will be kept in strict confidence for use in this research only. Confidentiality will be assured by the use of subject ID numbers rather than personal identifiers on questionnaires, blood collection and storage tubes. All subject paper records will be kept in locked file cabinets in the Medical Records Room at HNRCA and will be accessible only to the investigative team. The master list linking subject IDs to identifying information will be secured in a computer database. All data will be accessible only with a login and protected password. After the study is completed, all data will be kept in a locked file.

Subjects' records will be retained for a minimum of 10 years after the study is closed with the IRB.

Research related Injury

Emergency medical treatment will be given to participants if s/he is hurt or gets sick as a direct result of being in this research study. The participant or their insurance carrier will be asked to pay for any such medical care. There is no money to pay for the treatment if the participant gets hurt or sick as part of this study. The HNRCA does not have any money available to pay for a research-related injury or illness. If a participant experiences a research-related injury, they will be instructed to contact the Principal Investigator, [name], at [contact] or after hours or on weekends at [contact].

Economic Burden to Subjects

There will be no cost to the participant for participating in this study.

Vulnerable Populations

This study does not include vulnerable populations.

STATISTICAL CONSIDERATIONS

See Statistical Analysis Plan

Importance of Knowledge to be Gained

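### SAP 4.c plans the two primary comparisons with two different SDs (about 12% and 15%) for one outcome in the same 120 participants, and no single SD gives about 80% power for both

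*SAP*

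**What the plan says.** SAP 4.c bases the sample size on change in leg power from baseline to 24 weeks and plans two comparisons at the margins of the 2x2 table, 60 vs 60 each, two-sided alpha 0.05.

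- **KHCO₃:** 10% vs 4%, a difference of 6%. "We assumed a common standard deviation (SD) of change in power to be approximately 12" per cent, "based on the subset of men and women over age 65 in a previous study". The 60 vs 60 are said to "yield 80% power to detect a between-group difference of at least 6" per cent.
- **Whey:** 11% vs 3%, a difference of 8%. "We assumed a common SD of change in power to be 15" per cent. The 60 vs 60 are said to "yield 80% power to detect a between-group difference of at least 8" per cent. The source sentence concerns the effect only: "This effect size was observed when subjects in the previous study (1) were divided into high and low protein groups", by self-selected diet.

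SAP 7.b tests both effects in one ANCOVA of 24-week leg power, adjusted for baseline leg power, age, sex and the other intervention.

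The protocol does not help. SAP section 1 says that "several elements of the protocol, such as the sample size justification are reproduced here", but the protocol's Statistical Considerations section reads only "See Statistical Analysis Plan".

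**The concern.** The two comparisons are two ways of splitting the same 120 people on the same variable, and one model with one residual variance tests both. Apart from a small effect of averaging over the other factor, that population has one spread of change in leg power. Planning with about 12% for one split and 15% for the other uses two inputs that cannot both describe it.

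What is at stake is how a null result is read. A null KHCO₃ result will be judged against a stated type II error of 20% for a 6% difference. If the SAP's 15% were the right SD, that error would be about 42% before covariate adjustment. If 12% is right, the whey comparison has clearly more power than stated. The SAP does not say why the SDs differ or where the 15% came from.

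**Working it through.** **Inputs (SAP 4.c and Table 1).** Differences d = 6 (KHCO₃) and 8 (whey); SDs 12 and 15; n = 60 per margin; two-sided alpha 0.05. Table 1 cell means: 14 (both), 8 (whey only), 6 (KHCO₃ only), 0 (neither). All are percentage change in leg power.

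**Method.** Two-sample noncentral t with 118 df and noncentrality d / (SD × √(2/60)). Using 117 df, for a model that also contains the other factor, changes power by no more than 0.0002.

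**Step 1: reproduce the plan's figures.**
- KHCO₃: 6 / (12 × 0.1826) = 2.74, power 77.5% (78.2% by normal approximation). An SD of 11.6 gives 80%, which fits a value described as approximate.
- Whey: 8 / (15 × 0.1826) = 2.92, power 82.6% (83.2% by normal approximation). An SD of 15.5 gives 80%.

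Each statement roughly holds on its own SD.

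**Step 2: can the factorial layout explain two SDs?** Let s be the within-cell SD. In an unadjusted comparison, averaging over the other factor adds the square of half that factor's effect:
- KHCO₃ margin variance = s² + (8/2)² = s² + 16
- Whey margin variance = s² + (6/2)² = s² + 9

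The KHCO₃ variance should be larger by 7. The SAP has it smaller by 225 − 144 = 81. The layout therefore produces a far smaller gap, in the opposite direction. With s = 12 the margin SDs are √160 = 12.65 (KHCO₃) and √153 = 12.37 (whey).

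**Step 3: apply one SD to both.** Take it as the within-cell (residual) SD, which is what the two comparisons share once each is adjusted for the other factor.

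| Within-cell SD | KHCO₃, 6% | Whey, 8% | 80% detectable difference |
|---|---|---|---|
| 11.6% | 80% | 96% | about 6% |
| 12% | 77.5% | 95.2% | 6.2% |
| 15% | 58.4% | 82.6% | 7.7% |

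No row gives about 80% in both columns. For 80% power at 6%, each margin would need 64 at SD 12 and 100 at SD 15.

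**Step 4: sensitivity to what the SD means.**
- Without adjustment for the other factor, within-cell SDs of 12 and 15 give KHCO₃ margin SDs of 12.65 and √241 = 15.52, and power of about 73% and 56%.
- If 15 is instead the whey margin SD, the within-cell SD is √(225 − 9) = 14.70. KHCO₃ power is then about 60% adjusted for whey, or about 57% unadjusted (margin SD √232 = 15.23).

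The 15% scenario thus spans about 56% to 60%.

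**Step 5: covariate gain (assumption; the documents give no correlation).** If baseline, age and sex have multiple correlation r with the change score, the residual SD is 15 × √(1 − r²). For r = 0.3 it is 14.31 and KHCO₃ power is about 62%; for r = 0.5, 12.99 and about 71%; for r = 0.6, 12.0 and 77.5%.

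**The case against.** The strongest reply is that the 12% is the proper planning value and the KHCO₃ statement stands. It is the only SD with a stated source, that source is people over 65, and this trial enrols from age 65. On it, KHCO₃ power is 77.5% to 78.2%, consistent with 80% for an SD given as approximate. The 15% appears only beside the whey comparison, where it costs that comparison some stated power. This reply largely holds, and it decides how the 58% may be used. It does not remove the inconsistency: the SAP nowhere calls the 15% a cautious choice, and if it is a plausible SD for this outcome it is plausible for KHCO₃ too.

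A second reply is that the primary test is an ANCOVA on 24-week leg power, so neither change-score SD is the SD of that test. This also stands. All figures here come before any gain from baseline, age and sex, and that gain cannot be fixed from the documents.

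Third, the practical reach is limited. The SAP describes randomization in the past tense, and its Table 2 already reports the adjusted difference with a 95% confidence interval, which is the better guide to a null result. That limits the consequence, but the SAP still makes a power claim that a reader will cite.

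A reader might also infer a contradiction from the word common being used twice. The documents do not support that: it most naturally means common to the two arms of each comparison. The conflict lies in the two values.

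**Conclusion.** The point holds as an inconsistency of planning inputs. Two SDs are used for one outcome in one set of 120 participants, the 2x2 layout does not account for the difference, and the 15% has no stated source. With one within-cell SD, power for KHCO₃ and whey is about 78% and 95% at 12%, or about 58% and 83% at 15%. At least one of the stated 80% figures therefore misdescribes the trial: whey is understated if 12% applies, and KHCO₃ is overstated if 15% applies.

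Two stronger readings are tempting and should not be drawn. One is that the KHCO₃ comparison has only 58% power. That needs the unsourced 15% to override the sourced, age-matched 12%, and even then it is not the power of the planned ANCOVA. The other is that the sample size was miscalculated. Each calculation roughly reproduces from its own inputs.

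The figures rest on Table 1's additive effects, equal variance across the four cells, 60 analysed per margin, and no credit for baseline, age or sex. The point merits correction in the text; it does not threaten the analysis.

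**What to change.** Keep the existing planning paragraphs in SAP 4.c and add:

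> Both comparisons are tested in one model and share one within-cell (residual) SD. With 60 vs 60 and a two-sided 0.05 test, adjusting for the other factor but before any gain from baseline, age and sex, a within-cell SD of 12% gives about 78% power for 6% (KHCO₃) and 95% for 8% (whey), with an 80% detectable difference of 6.2%. A within-cell SD of 15% gives about 58% and 83%, with an 80% detectable difference of 7.7%. The planning SD is [12% or 15%], from [source]; the 15% was taken from [source].

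The text should say within-cell SD. Calling it the SD of the unadjusted margins would add a new inconsistency, because those margins differ slightly from each other (Step 2). If the sponsor wishes to claim a gain from covariate adjustment, the assumed correlation should be stated.

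The cost is a few sentences. Sample size, primary model, alpha, analysis sets and the Table 2 shell do not change. The only downside is a less favourable stated power for KHCO₃.

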9. significant immune disorder
10. current unstable heart disease
11. Crohn's disease
12. active malignancy or cancer therapy in the last year
13. alcohol use exceeding 2 drinks/day
14. current peptic ulcers or esophageal stricture
15. milk protein allergy
16. other condition or abnormality in screening labs, at discretion of the study physician ([name])

Withdrawal of subjects:

Participants are free to stop participation at any time for any reason. Should a participant decide to withdraw from the study, the study measurements made prior to withdrawal may be included in the scientific analysis and publication of the study results. Upon completion of the study and data analysis, which may take up to

four years, any remaining blood samples will be discarded. To withdraw from the study, a participant can contact the study PI ([name]).

RECRUITMENT AND RETENTION

This team has successfully recruited for KHCO₃ intervention trials. In our dose-finding KHCO₃ trial, we recruited and enrolled 244 older adults over a 31-month period,²⁵ completing enrollment 7 months ahead of schedule. Recruitment will be done in ways that have been successful for us in the past, including:

Local recruitment methods:

- 1) We will identify appropriate potential candidates (i.e., those who meet our age criteria and whose participation in prior studies would not make them ineligible) in the HNRCA Recruitment database, and send them a recruitment letter and an email. We will also send a modified recruitment letter and email to potential candidates who received a recruitment letter for this study >1 year ago, to reassess their interest. Interested individuals may call or reply via email for more information about the study and their potential eligibility (opt in). A follow up call or email will be made to those people who do not reply. A voicemail will be left for those who do not answer the telephone.

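### SAP 5.b item 4 makes withdrawal of consent for future data collection a ground for exclusion from the mITT set, so valid week-12 measurements leave the mITT repeat analyses while those of comparable participants lost to follow-up stay

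*SAP*

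**What the plan says.** SAP 5.b gives four major protocol deviations. The fourth is "Withdrawal of consent for future data collection, and/or ongoing use of previously collected study data". It covers two events: stopping further collection, and revoking the use of data already held.

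SAP 5.c then defines three sets.
- ITT: "The full analysis set will include all randomized subjects".
- mITT: the ITT sample without participants who took under 10% of product and without "those with any major protocol deviation".
- Per protocol: "we will further restrict the mITT sample to participants who took whey protein isolate" and KHCO₃ throughout the 24 weeks, with average compliance of at least 75%.

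On their use, SAP 7.b states "Primary analyses of the primary outcome will be performed on the ITT sample". The other two sets appear only under secondary analyses: "We will repeat analyses in the mITT and per protocol samples".

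The Protocol, under Withdrawal of subjects, says that after a participant withdraws "the study measurements made prior to withdrawal may be included in the scientific analysis and publication of the study results".

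**The concern.** Withdrawal of consent for future collection tells us that later values will be missing. It casts no doubt on values already obtained. Treating it as a major deviation removes the whole participant from mITT, including a week-12 visit that was attended and measured properly.

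Withdrawal happens after randomisation and could depend on assigned treatment or on how the participant was doing. Excluding on it makes mITT a selected subset. It also removes the partial records that a missing-at-random analysis (SAP 7.d) relies on. Participants who leave without formally withdrawing consent are not caught by item 4, so handling turns on how someone left and not on what was measured. At stake is how far the mITT results can be read as a check on the ITT results for week-12 outcomes and for the longitudinal model.

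**Working it through.** No figure in the plan depends on this point. For context, the stated 80% power reproduces approximately, using Φ(difference/SE − 1.96) with SE = SD × √(2/60):
- KHCO₃: 6/(12 × 0.1826) = 2.739, giving 78.2%.
- Whey: 8/(15 × 0.1826) = 2.921, giving 83.2%.

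Both concern the 24-week change in the randomised comparison, and item 4 does not alter them.

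**Following the rules through.** Take two participants in the same arm, each with adequate product intake, baseline and week-12 tests, and no week-24 test. A is lost to follow-up. B withdraws consent for further collection after week 12.

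| Analysis | A | B |
|---|---|---|
| ITT, week 12 and longitudinal | in | in |
| ITT, week-24 ANCOVA (observed data) | no value | no value |
| mITT, week-12 outcomes | in | **out** |
| mITT, longitudinal model | in, through week 12 | **out** |
| mITT, imputation if repeated there | in, week 24 imputed | **out** |
| mITT, week-24 ANCOVA (observed data) | no value | no value |

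The three marked rows are the whole effect. The week-12 outcomes concerned are leg-press peak power at 70% and 40% of 1-RM and knee-extension peak torque (SAP 7.a).

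**How large could it be?** The documents give no withdrawal rate, so these inputs are assumptions: 65 participants per whey margin with week-12 data; 10 later consent withdrawals in all; withdrawers 8 points lower than stayers in week-12 change. The SD of 15 is the SAP's whey figure (SAP 4.c), borrowed from the 24-week change.

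Shift in the contrast from dropping withdrawers = deficit × (withdrawn on whey/65 − withdrawn on placebo powder/65).
- 8 on whey, 2 on placebo powder: 8 × 8/65 − 8 × 2/65 = 0.98 − 0.25 = +0.74 points.
- 2 and 8: −0.74 points.
- 5 and 5: 0.
- 8 and 2 with half the deficit (4 points): 4 × 6/65 = +0.37 points.

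Standard error before exclusion: 15 × √(2/65) = 2.63. After exclusion in the 8-and-2 case (57 and 63 left): 15 × √(1/57 + 1/63) = 2.74, a rise of about 4%. The 0.74-point shift is 0.74/2.63 = 0.28 standard errors. I use the standard error as the yardstick because the SAP's hypothesised 8-point whey effect is for 24 weeks and is not a fair denominator for a week-12 shift.

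**The case against.** The strongest reply is that little depends on this. The pre-withdrawal data remain in the ITT set, which carries the primary analysis; the mITT set only repeats analyses. The likeliest route to unequal withdrawal, intolerance of the products, is also partly closed. Under Protections Against Risk and Protection of study blinding, the Protocol keeps participants who cannot tolerate the full amount in the study, and encourages those who stop product to complete measurements, except after a serious adverse event. Its only tolerability counts, from the earlier KHCO₃ trial, show 2 participants on placebo, 1 on 81 mmol/d and 2 on 122 mmol/d stopping pills for gastrointestinal complaints. That suggests no excess at this trial's dose, and there are no figures for whey. All of this stands, and it limits the size. It does not explain why A and B should be handled differently.

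A reader might also infer more than the documents support:
- **That usable data are lost to the trial.** They are lost only to the mITT repeats.
- **That the SAP contradicts the Protocol.** The Protocol wording is permissive and does not require inclusion in every supportive set.
- **That the per-protocol set is damaged too.** It already requires product throughout the 24 weeks, so someone who withdraws soon after week 12 would ordinarily fail it anyway.
- **That data whose use was revoked must stay in the primary analysis.** The ITT definition settles who belongs to the set. It does not order the use of revoked data, and the reference in SAP 7.d to all available data can be read to leave them out. Consent pages were not available for this review and may cover it. This is missing detail, not a stated rule.

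**Conclusion.** The point holds for the mITT set. Item 4 selects that set on a post-randomisation event and discards valid week-12 values from three kinds of mITT analysis. The primary ITT analysis, its stated power and the complete-case week-24 mITT ANCOVA are untouched.

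The size cannot be determined from the documents. Bias is nil if withdrawal is balanced and withdrawers differ from stayers equally in each arm; then only precision is lost. Even the lopsided illustration moves a supportive week-12 estimate by under a third of a standard error, and its split, deficit and sample size are all assumed. This is a free improvement of small expected effect, not a threat to the trial's main conclusion.

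**What to change.** In SAP 5.b and 5.c, remove withdrawal of consent for future data collection from the major deviations that exclude from mITT. State that measurements made before withdrawal remain in mITT. Withdrawals would still be tabulated under SAP 6.c. Leave the per-protocol definition unchanged.

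Optional clarification: state that data whose use a participant has withdrawn are removed from every analysis set, and count such cases by arm in the CONSORT diagram.

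The cost is a line or two of wording and no new data. The change belongs before outcome data are examined by group, in keeping with the SAP's purpose in section 1.
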